9.3 Immunogenicity

Anti-drug (UCB6114) antibody status and classification, changes from Baseline in titer over time (Cycles 1, 2 and even cycles thereafter) and the incidence of treatment-emergent ADA positivity are exploratory immunogenicity endpoints in Part C of this study. Potential relationships between ADA and PK, PD, antitumor activity and safety will also be explored but this will be reported separately outside of the CSR.

Serum samples will be collected from all study participants for the measurement of ADA and the evaluation of immunogenicity according to the Schedule of Activities in the protocol.

All listings of ADA will be presented for the SS and summaries of the ADA data will be presented by treatment group for the ADAS.

Anti-drug (UCB6114) antibodies will be measured using a three-tiered assay approach: Screening assay, confirmatory assay and titration assay.

Samples will first be evaluated in the Screening assay using a false positivity rate of 5% (reported as ‘negative screen’ or ‘positive screen’), followed by analysis of screened positive samples in the confirmatory assay (which is a drug depletion assay) to confirm the positivity of the samples (reported as ‘negative immunodepletion’ or ‘positive immunodepletion’). Samples that are confirmed as positive in the confirmatory assay will be evaluated in a titration assay to assess the ADA level and this will be reported as titer (reciprocal dilution factor including minimum required dilution).

Anti-drug (UCB6114) antibody sample status will be determined as follows from the pre-treatment sample taken on Day 1 of Cycle 1 (Baseline) and all post-treatment (post-Baseline) samples.

- Sample values that are either ‘negative screen’ or ‘positive screen’ and ‘negative immunodepletion’ will be defined as **ADA negative**
- Sample values that are ‘positive screen’ and ‘positive immunodepletion’ will be defined as **ADA positive**

Anti-drug (UCB6114) antibody sample status will be listed for each participant at each visit by treatment group. This listing will include sampling dates and times, the Screening assay result, the confirmatory assay result and the derived ADA sample status. In addition, the titer from the titration assay (if applicable) will be listed together with the change from Baseline in titer. The number and percentage of participants with a positive or negative sample at each visit will be summarized by treatment group. Percentages will be calculated based on the number of participants with a non-missing/sufficient sample at the visit.

Based on the ADA status of the samples, study participants will be categorized according to the following 6 ADA classifications in [Table 9-2](#):

Table 9-2: ADA Classifications

Classification	Classification Label	Definition
1	Pre-ADA negative – treatment induced ADA negative	Includes participants who have an ADA negative status at Baseline, or missing/insufficient Baseline sample, and an ADA negative status at all sampling timepoints post-Baseline (including SFU). Participants with missing post-Baseline samples are included as long as the missing samples do not result in an unmonitored period greater than 16 weeks.
2	Pre-ADA negative – treatment induced ADA positive	Includes participants who have an ADA negative status at Baseline, or missing/insufficient Baseline sample, and an ADA positive status at any sampling timepoint post-Baseline (including SFU).
3	Pre-ADA positive – treatment reduced ADA	Includes participants who have an ADA positive status at Baseline and an ADA negative status at all sampling timepoints post-Baseline (including SFU).
4	Pre-ADA positive – treatment unaffected ADA	Includes participants who have an ADA positive status at Baseline and an ADA positive status at any sampling timepoint post-Baseline (including SFU) with titer values of the same magnitude as Baseline (≤ 1.80 fold difference from the Baseline value) or with decreased titer values compared to Baseline (> 1.80 fold decrease from the Baseline value).
5	Pre-ADA positive – treatment boosted ADA positive	Includes participants who have an ADA positive status at Baseline and an ADA positive status at any sampling timepoint post-Baseline (including SFU) with increased titer values compared to Baseline (> 1.80 fold increase from the Baseline value).
6	Inconclusive	Includes participants who do not satisfy the criteria for classifications 1-5.

ADA=anti-drug (UCB6114) antibody; SFU=Safety Follow-up.

Note: The terminology 'treatment unaffected' is ambiguous as the criteria refers to ADA responses that are not increased upon dosing compared to Baseline level whereas titers may reduce.

A study participant will be classified as having **treatment-emergent ADA positivity** if they satisfy one of the following criteria:

- The Baseline result is ADA negative and at least one post-Baseline result is ADA positive (pre-ADA negative – treatment induced ADA positive) – ADA classification 2 in [Table 9-2](#);
- The Baseline result is ADA positive and at least one post-Baseline result shows a pre-defined fold increase in titer from the Baseline value (the fold increase from Baseline required to meet this criterion will be defined with the development of the assay and will be included in the TFLs) (pre-ADA positive – treatment boosted ADA positive) – ADA classification 5 in [Table 9-2](#).

Total anti-drug (UCB6114) antibody **incidence** will be determined by the number and percentage of participants with treatment-emergent ADA positivity (as defined above). The denominator for the percentage calculation will be the number of participants with at least one available/reported post-Baseline result.

Total **prevalence** of pre-anti-drug (UCB6114) antibody will be determined by the number and percentage of participants who are pre-ADA positive (i.e. participants who have a positive ADA status at Baseline). The denominator for the percentage calculation will be the number of participants with an available/reported Baseline sample result.

Total anti-drug (UCB6114) antibody **prevalence** will be determined by the number and percentage of participants with ADA classifications 2, 3 or 5 in [Table 9-2](#) (i.e. an ADA positive status at any post-Baseline sampling timepoint). The denominator for the percentage calculation will be the number of participants with at least one available/reported sample result (either at Baseline and/or post-Baseline).

The ADA classification for each participant will be listed by treatment group. This listing will also include whether or not the participant achieved treatment-emergent ADA positivity (ADA incidence), whether the participant was pre-ADA positive (pre-ADA prevalence) and whether the participant had an ADA positive or negative status at any post-Baseline sampling timepoint (ADA prevalence). In addition, the visit at which the participant first achieved treatment-emergent ADA positivity will be included.

The number and percentage of participants in each of the 6 ADA classifications defined above in [Table 9-2](#) will be presented by treatment group. Also, in this tabulation, ADA incidence and prevalence (as defined above) will be summarized.

The first occurrence of treatment-emergent ADA positivity (based on the criteria above) will be summarized using frequency counts and percentages at each post-Baseline visit by treatment group. This tabulation will include a count of the number of participants at each post-Baseline visit who fulfill at least one of the above defined criteria for treatment-emergent ADA positivity; participants will be counted in the numerator based on the earliest visit at which one of these criteria is fulfilled. At other visits, participants will be counted in the denominator (assuming an assessment of treatment-emergent positivity is available) and this will be used in the percentage calculations.

Individual study participant ADA titer profiles over actual time will be presented graphically on the linear and the semi-logarithmic scale. The linear scale plots will be repeated for the subset of participants who achieve treatment-emergent ADA positivity during Part C.

Mean (\pm standard deviation) C_{min} will be plotted by ADA sample status over nominal (scheduled) time with treatment groups overlaid on the same plot. On this plot, mean C_{min} at Cycle 1 Day 15 will be the mean of the derived C_{min} following the first dose of UCB6114 (as described in [Section 9.1.2](#)) and, thereafter from Cycle 2 Day 1, mean C_{min} will be the mean of the predose concentrations at the subsequent dosing visits.

10. EFFICACY ANALYSES

10.1 Antitumor activity

The analysis of antitumor activity is exploratory in Part C of this study.

10.1.1 Definitions of the antitumor activity endpoints

The following endpoints are defined based on RECIST (Version 1.1) which standardizes solid tumor measurements and provides guidelines for the objective assessment of changes in tumor size during anti-cancer treatment.

Appendix 9 (Section 11.9) of the protocol contains the RECIST 1.1 guidelines to be used in this study, adapted from Eisenhauer (2009), and includes the definitions of target and non-target lesions, the definitions of target and non-target lesion responses at each tumor assessment, the criteria for determining overall response at each tumor assessment based on target lesion response, non-target lesion response and the presence/absence of new lesions, and a participant's best overall response (BOR). Further details on the rules to apply in the derivation of BOR are included in the Derivation of Efficacy Endpoints document which has been developed to support this SAP.

At each post-Baseline tumor assessment, the investigator will record responses for target lesions and non-target lesions, whether or not there has been an appearance of any new lesions, and the participant's overall response based on their target lesion response, non-target lesion response and the presence/absence of new lesions. Note that target lesion response and non-target lesion response assessments will be based on the changes in the pre-existing lesions at Baseline and the appearance of new lesions will only factor in the determination of an overall response of PD at that tumor assessment visit (i.e. per Tables A and B in Section 11.9.2 of Appendix 9 of the protocol).

Objective response rate (ORR) is defined as the percentage of participants with a BOR of complete response (CR) or partial response (PR) during Part C.

Disease Control Rate (DCR) is defined as the percentage of participants with a BOR of CR, PR, or stable disease (SD) during Part C.

Best overall response (BOR) is defined for each study participant as the best overall tumor response from each tumor assessment (performed every 8 weeks from Day 1 of Cycle 1 (\pm 7 days)) according to the RECIST criteria for changes in target and non-target lesions and the appearance of new lesions. Best overall response is determined from the start of study treatment (first dose of UCB6114) until documented objective disease progression or the date of

subsequent anti-cancer therapy (systemic therapy, surgery or radiotherapy for cancer), whichever occurs first. If anti-cancer therapy is started on the same day as a tumor assessment, then the overall response from that assessment will be used in the derivation of BOR. If a participant does not have objective disease progression or does not start a subsequent anti-cancer therapy then all tumor assessments up to the SFU visit will be included in the derivation of BOR. For a BOR of SD, a participant's tumor measurements must have met the SD criteria at least once after the start of study treatment at a minimum interval of no less than 49 days.

For this study, BOR determination requires confirmation of CR or PR responses at a subsequent assessment ≥ 4 weeks (28 days) after the criteria for CR or PR responses are first met, however, an unconfirmed BOR will also be derived for each participant for the purpose of reporting (as described below in [Section 10.1.2](#)). Table C in Appendix 11.9 of the protocol and Table 1 and subsequent text in the Derivation of Efficacy Endpoints document provides the derivation of BOR when confirmation of CR and PR responses are required. The definition of an unconfirmed BOR is also included in this document. Although the derivation of unconfirmed BOR does not include the requirement for a CR or PR response to be confirmed ≥ 4 weeks (28 days) after the initial response, a participant's CR or PR response may, in fact, be confirmed at a subsequent assessment ≥ 4 weeks (28 days) after the criteria for the CR or PR response are first met. Unconfirmed BOR will be referred to as BOR (confirmed or unconfirmed) throughout the rest of this document.

Confirmed BOR and BOR (confirmed or unconfirmed) will be derived programmatically based on the overall tumor assessment data recorded on the eCRF by the investigator.

Duration of response (DOR) will be calculated for participants with a BOR of confirmed CR or PR as the time in days from the start date of the confirmed CR or PR (e.g. the date of the first overall response of CR or PR, which is at least 4 weeks before a second overall response of CR or PR) to the first date that recurrent or progressive disease is objectively documented (i.e. according to the RECIST guidelines). This will be referred to as the duration of confirmed response and the following calculation will be performed:

$$\begin{aligned} & \text{Duration of Confirmed Response} \\ &= (\text{Date of First Objective Disease Progression} \\ &\quad - \text{Start Date of Confirmed CR or PR Response}) + 1 \end{aligned}$$

Duration of response will also be calculated for participants with a BOR of CR or PR which is either confirmed or unconfirmed [DOR (confirmed or unconfirmed)] as the time in days from the start date of the CR or PR to the date of the first documented objective disease progression (i.e. according to the RECIST guidelines). The following calculation will be performed:

$$\begin{aligned} & \text{DOR (Confirmed or Unconfirmed)} \\ &= (\text{Date of First Objective Disease Progression} \\ &\quad - \text{Start Date of CR or PR Response}) + 1 \end{aligned}$$

For the purpose of a sensitivity analysis of both duration of confirmed response and DOR (confirmed or unconfirmed), the above calculations will take into consideration the occurrence of both objective disease progression (per RECIST 1.1) and clinical disease progression (as described in Appendix 11.9 of the protocol and as determined by the investigator and recorded as a reason for study treatment discontinuation on the eCRF), whichever occurs first. If clinical

disease progression occurs on the same date that a participant's objective disease progression is determined, then the participant will be included in the sensitivity analyses as having objective disease progression.

The following calculations will therefore be performed for the sensitivity analyses:

$$\begin{aligned} \text{Duration of Confirmed Response} \\ = & (\text{Date of First Objective or Clinical Disease Progression} \\ & - \text{Start Date of Confirmed CR or PR Response}) + 1 \end{aligned}$$

$$\begin{aligned} \text{DOR (Confirmed or Unconfirmed)} \\ = & (\text{Date of First Objective or Clinical Disease Progression} \\ & - \text{Start Date of CR or PR Response}) + 1 \end{aligned}$$

For participants who die without objective disease progression, DOR will be censored on the date of death, regardless of cause. For a participant who discontinues early from Part C of the study with no objective disease progression, DOR will be censored on the date of their last available (scheduled or unscheduled) tumor assessment at which a lack of objective disease progression was determined. Participants who discontinue study treatment but who do not have documented objective disease progression (i.e. according to the RECIST guidelines), DOR will be censored at the date of their last available (scheduled or unscheduled) tumor assessment at which a lack of objective disease progression was determined. Such participants might include those that are ongoing in Part C at the time of any defined data cut-off. Likewise, participants who have not discontinued early and do not have disease progression after a confirmed or unconfirmed response, DOR will be censored at the date of their last available (scheduled or unscheduled) tumor assessment.

In the sensitivity analyses of duration of confirmed response and duration of unconfirmed response, the same censoring rules will apply except that the date of last contact will be used for the censoring of participants who discontinue early from Part C or complete Part C without objective disease progression, clinical disease progression or death.

Date of last contact will be the latest of the dates of premature study termination and of last contact recorded on Study Termination eCRF page, the date of death, the date of last dose of study treatment, the dates of all visits, AE start and end dates (with partial dates imputed as earliest possible) and the date of contact recorded on the Survival Safety Follow-up and Survival Final Follow-up eCRF forms.

Further details on the rules to apply in the derivation of DOR are included in the Derivation of Efficacy Endpoints document which has been developed to support this SAP.

Progression-free survival (PFS) will be calculated as the time in days from the first dose of study treatment to the date of the first documented objective disease progression (i.e. according to the RECIST guidelines), or death due to any cause, whichever occurs first. The following calculation will be performed:

$$\text{PFS} = (\text{Date of Objective Progressive Disease/Death} - \text{Date of First Dose}) + 1$$

Participants who die due to any cause without a documented objective disease progression will be considered to have progressed on the date of their death. Participants who do not have any post-Baseline tumor assessments will be censored on the date of their first dose of study treatment. Participants who discontinue early from Part C or discontinue study treatment without

documented objective disease progression or death, will be censored on the date of their last available (scheduled or unscheduled) tumor assessment at which a lack of objective disease progression was determined. Participants who start anti-cancer therapy during Part C without a prior documented objective disease progression will be censored on the date of their last available (scheduled or unscheduled) tumor assessment prior to the initiation of the subsequent anti-cancer therapy. If anti-cancer therapy starts on the same date as the participant's tumor assessment and determination of objective disease progression, or the participant's death (due to any cause), then the participant will not be censored and the participant will be included as having an uncensored event on this date. This censoring rule will also be applied to participants who are ongoing at any data cut-off for an analysis of Part C data who have no documented objective disease progression. The use of anti-cancer therapy during Part C will be identified via ongoing medical review of the concomitant medications together with the start dates of further anti-cancer therapy information recorded on the survival follow-up pages of the eCRF.

As a sensitivity analysis, PFS will also be calculated as the time in days from the first dose of study treatment to the date of the first documented objective disease progression (per RECIST 1.1), the date of clinical disease progression, as determined by the investigator, or the date of death due to any cause, whichever occurs first. Last contact date will be used for the censoring of participants still alive with no reported disease progression (objective or clinical). The same rules described above for the censoring of participants who start anti-cancer therapy will be applied in this sensitivity analysis.

Further details on the rules to apply in the derivation of PFS are included in the Derivation of Efficacy Endpoints document which has been developed to support this SAP.

Overall survival (OS) will be calculated as the time in days from the date of first dose of UCB6114 to the date of death from any cause. Participants will be followed up to ascertain their survival status at the SFU visit (within 30 days after their last dose of UCB6114) and at the Final Visit (3 months after their last dose of UCB6114); they will not be followed up beyond this timepoint.

The following calculation will be performed:

$$OS = (Date of Death - Date of First Dose of UCB6114) + 1$$

OS will be censored on the date of their last contact for participants who discontinue early from Part C of the study or who discontinue study treatment due to disease progression but continue in the study, are not known to have died.

Further details on the rules to apply in the derivation of OS are included in the Derivation of Efficacy Endpoints document which has been developed to support this SAP.

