Participants who die due to any cause without a documented objective disease progression will be considered to have progressed on the date of their death. Participants who do not have any post-Baseline tumor assessments will be censored on the date of their first dose of UCB6114. Participants who discontinue early from Part B or discontinue study treatment without

documented objective disease progression or death, will be censored on the date of their last available (scheduled or unscheduled) tumor assessment at which a lack of objective disease progression was determined. Participants who start anti-cancer therapy during Part B without a prior documented objective disease progression will be censored on the date of their last available (scheduled or unscheduled) tumor assessment prior to the initiation of the subsequent anti-cancer therapy. If anti-cancer therapy starts on the same date as the participant's tumor assessment and determination of objective disease progression, or the participant's death (due to any cause), then the participant will not be censored and the participant will be included as having an uncensored event on this date. This censoring rule will also be applied to participants who are ongoing at any data cut-off for an analysis of Part B data who have no documented objective disease progression. The use of anti-cancer therapy during Part B will be identified via ongoing medical review of the concomitant medications together with the start dates of further anti-cancer therapy information recorded on the survival follow-up pages of the eCRF.

As a sensitivity analysis, PFS will also be calculated as the time in days from the first dose of UCB6114 to the date of the first documented objective disease progression (per RECIST 1.1), the date of clinical disease progression, as determined by the investigator, or the date of death due to any cause, whichever occurs first. Last contact date will be used for the censoring of participants still alive with no reported disease progression (objective or clinical). The same rules described above for the censoring of participants who start anti-cancer therapy will be applied in this sensitivity analysis.

Further details on the rules to apply in the derivation of PFS are included in the Derivation of Efficacy Endpoints document which has been developed to support this SAP.

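### A scan on the day new anti-cancer therapy starts counts for PFS if it shows progression but, read literally, not if it shows response or stable disease; BOR uses it either way

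*SAP*

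**What the plan says.** Section 10.1.1 of the Part B and Part C SAPs gives several rules that meet when a tumor assessment and the start of new anti-cancer therapy share a date.

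- **PFS, new therapy.** A participant who starts such therapy with no progression documented before it "will be censored on the date of their last available (scheduled or unscheduled) tumor assessment prior to the initiation of the subsequent anti-cancer therapy".
- **PFS, same-date exception.** If new therapy starts on the date of a scan at which objective progression is determined, or on the date of death, "then the participant will not be censored and the participant will be included as having an uncensored event on this date". No sentence covers a same-date scan without progression.
- **PFS, treatment stopped.** Participants who discontinue study treatment or the study without progression or death are censored at their last assessment showing no progression.
- **PFS, floor.** In Part C, "Participants who do not have any post-Baseline tumor assessments will be censored on the date of their first dose of study treatment". Part B has the same rule, anchored to the first dose of UCB6114.
- **BOR.** "If anti-cancer therapy is started on the same day as a tumor assessment, then the overall response from that assessment will be used". The result of the scan does not matter.

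The sensitivity PFS, which adds clinical progression as an event, keeps the same new-therapy censoring. Section 10.1.2 summarizes PFS by Kaplan-Meier, by treatment group, with event and censoring counts, minimum and maximum, and rates at 3, 6 and 9 months.

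**The concern.** Whether a same-day scan enters the PFS analysis depends on what it shows. If it shows progression, the participant is at risk on that day and has an event. If it does not, the participant leaves the risk set at the previous scan. Observed progression-free time is discarded only for those who did not progress, which is censoring that depends on the outcome.

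The rules also give inconsistent results for one person. A same-day scan can make a participant a responder, or count as disease control, in ORR or DCR while PFS stops one scan earlier. Someone moving to new therapy has usually stopped study treatment too. The treatment-stopped rule then gives the same-day scan and the new-therapy rule gives the one before it. Section 10.1.1 states no precedence, so two programmers could derive different dates. The sensitivity PFS carries the same rule and would not reveal the problem.

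**Working it through.** The SAPs state no PFS estimate, event count or power figure, so there is nothing to reproduce. Section 10.1.2 gives scans every 8 weeks, with the first at Day 57 ± 7 days (Day 50 to 64). This agrees with 1 + 56 = 57, and the next scan is nominally at 57 + 56 = Day 113.

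**1. What 'prior' means.** The new-therapy rule applies to participants without a prior documented progression. If 'prior' included the same date, a same-date progression would already fall outside the rule and the progression half of the exception would be unnecessary. The exception makes sense only if 'prior' means strictly earlier. A same-day scan without progression is then not prior to the new therapy, and nothing brings it back in.

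**2. The rules side by side, for a scan on the therapy start date.**

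| Rule in 10.1.1 | Scan shows progression | Scan shows CR, PR or SD |
|---|---|---|
| PFS, new therapy | event on that date | censored at the previous scan |
| PFS, treatment stopped | not applicable | censored at that scan |
| BOR | scan used | scan used |

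**3. Effect on one participant.** PFS = (date − date of first dose) + 1. Suppose there is a scan without progression at Day 113, with new therapy starting that day and an earlier scan at Day 57. Using the same-day scan gives 113 days. The literal rule gives 57. The loss is 113 − 57 = 56 days.

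**4. Effect on Kaplan-Meier at one scan.** With n at risk, d progressions at the scan and c same-day non-progressors, and with times censored at the scan counted as at risk there:

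- same-day scan used: 1 − d/n
- literal rule: 1 − d/(n − c)

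| n | d | c | Literal | Same-day scan used |
|---|---|---|---|---|
| 9 | 2 | 1 | 6/8 = 75.0% | 7/9 = 77.8% |
| 9 | 3 | 1 | 5/8 = 62.5% | 6/9 = 66.7% |
| 27 | 9 | 1 | 17/26 = 65.4% | 18/27 = 66.7% |

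Nine is the maximum number of evaluable participants per dose level and 27 the maximum enrolment per part (sections 2.3 and 2.4). The values of d and c are illustrative. The direction is general: moving a non-event back one scan can only shrink the risk set at later event times, so every Kaplan-Meier factor is equal or lower.

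**5. Effect over several scans.** This was simulated with 27 participants, scans every 56 days and 1000 trials per setting. The progression probability per interval and the probability q of starting new therapy on the day of a non-progressing scan are assumptions, not SAP figures. Kaplan-Meier PFS at 6 months (Day 182), in %:

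| Progression per interval | q | Literal | Same-day scan used | Difference |
|---|---|---|---|---|
| 0.30 (true 34.30) | 0.02 | 33.49 | 34.13 | 0.64 |
| | 0.05 | 32.30 | 33.90 | 1.60 |
| | 0.10 | 31.56 | 34.72 | 3.16 |
| | 0.20 | 27.70 | 34.42 | 6.72 |
| 0.45 (true 16.64) | 0.02 | 16.37 | 16.84 | 0.47 |
| | 0.05 | 15.31 | 16.42 | 1.11 |
| | 0.10 | 13.91 | 16.10 | 2.19 |
| | 0.20 | 12.42 | 17.07 | 4.65 |

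The literal rule exceeded the alternative in no simulated trial.

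**6. The floor.** The first-dose rule covers only participants with no post-Baseline scan at all. It does not literally cover someone whose only post-Baseline scan falls on the therapy start date, or someone who starts new therapy before the first scan and is scanned later. If Screening (up to 28 days before dosing, section 3.2.3) were taken as the last assessment, the formula would give −28 + 1 = −27 to −1 + 1 = 0 days. Censoring at first dose gives 0 + 1 = 1 day. Either way the participant is gone before the first scan, and the simulated Kaplan-Meier values were identical. Only a death on Day 1 itself could make a difference.

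**The case against.** The SAPs never say that a same-day scan without progression is ignored. The text refers to the initiation of therapy, and a scan done that morning precedes a dose given that afternoon. The treatment-stopped rule would also pick up such a scan. Section 10.1.1 sends further PFS rules to the Derivation of Efficacy Endpoints document, which is not shown and may settle same-day ties. Participants continue treatment until progression, unmanageable toxicity or withdrawal of consent, so a non-progressor starting new therapy on a scan day should be uncommon. PFS is exploratory, descriptive and produced only if the data allow.

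Much of this stands. The frequency is unknown and probably low, no formal decision rule uses PFS, and the derivation document may already hold the answer. The reading of the text is less persuasive. The rule works from start dates, which do not order events within a day, and the same-date exception for progression is redundant unless 'prior' means strictly earlier. The treatment-stopped rule shows that two rules disagree; it does not say which prevails.

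A reader might also infer that PFS is planned to be zero or negative for some participants. The documents do not support that. It requires Screening to count as the last available assessment, yet sections 4.3 and 10.1.2 use the scheduled-or-unscheduled wording for post-Baseline scans, Table 3-1 makes Screening the Baseline value, and the first-dose rule shows the intended minimum.

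**Conclusion.** The point holds as a minor defect of wording with a known direction. Read literally, the PFS rule in both SAPs uses a same-day scan when it shows progression and drops it when it does not. This contradicts the BOR rule and the neighbouring PFS censoring rule in the same section.

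The effect on Kaplan-Meier PFS can only be downward. One affected participant among nine with two progressions at Day 57 costs 2.8 percentage points (77.8 − 75.0). Under the assumed rates, the 6-month estimate falls by about 0.5 to 1.6 points when 2 to 5% of non-progressing scans coincide with a start of new therapy, and by about 2 to 7 points at 10 to 20%. The SAPs give no such rate, so it would be wrong to infer that PFS will be materially biased.

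The gap in the first-dose floor is secondary. It could put a non-positive time in a listing or in the reported minimum if programmed literally, but it does not alter the Kaplan-Meier estimate in practice.

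**What to change.** In section 10.1.1 of both SAPs, for the main and the sensitivity PFS:

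1. Reword the new-therapy rule so that participants are censored at the last tumor assessment showing no progression *on or before the start date* of the subsequent therapy. Keep the same-date exception for progression and death. For a same-day scan, the rule then agrees with BOR and with the treatment-stopped rule.
2. Add that participants with no post-Baseline assessment on or before that date are censored on the date of first dose.

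Both changes are needed: the second prevents non-positive times but leaves the asymmetry in place. Check that the Derivation of Efficacy Endpoints document says the same. The cost is two sentences in each SAP and a small change to the PFS derivation, with no new data.
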